2. ABBREVIATIONS AND DEFINITIONS

2.1 Abbreviations

AE	Adverse event
ALS	Amyotrophic Lateral Sclerosis
CRF	Case Report Form
CRO	Contract Research Organization
CSF	Cerebrospinal fluid
DPIA	Data Protection Impact Assessment
EC	Ethics Committee
ELISA	Enzyme-Linked Immunosorbent Assay
GCP	Good Clinical Practice
ICF	Informed Consent Form
ICH	International Conference on Harmonization
PI	Principal Investigator
SOP	Standard Operating Procedure
CTC	Clinical Trial Center
OSR	Ospedale San Raffaele

2.2 Definitions

MESO	ELISA Meso-scale Discovery Platform
------	-------------------------------------

3. STUDY DESCRIPTION AND RATIONALE

Amyotrophic lateral sclerosis (ALS) is an adult-onset progressive, fatal, neurodegenerative disorder that results in the gradual degeneration of the motor neurons in the motor cortex and spinal cord. ALS is the most common type of motor neuron disease with an incidence rate of 2.8 per 100,000 persons/year and a mean prevalence rate of 5.4 per 100,000 people in Europe. ALS is characterized by rapidly progressive paralysis and death typically occurs from respiratory failure within 2 to 4 years of symptom onset, although about 10% of ALS patients manifest a slow form of the disease with a survival of 10 years or longer (1). Clinical diagnosis of ALS is often a prolonged process due to heterogeneity in patient presentation and prognosis as well as a lack of specific diagnostic, prognostic and the diagnostic biomarkers. This is a recognized critical bottleneck for both ALS translational research and clinical applications. The importance of biomarker discovery for therapeutic advancement is underscored by the recent accelerated approval of QALSYD (Tofersen) for treatment of SOD1-ALS patients, a decision that was primarily based on reduction in plasma Nf-L in treated patients. Nevertheless, despite its value, an increase in circulating Nf-L (2,3) following neuro-axonal damage represents a late pathogenic event also found in other neurological disorders besides ALS. The ideal fluid biomarker for ALS would be capable to sensitively monitor early disease manifestation, treatment responses and dynamic pathogenetic events, features that are not met by Nf-L. Other potential biomarkers of neuronal damage in ALS include tau (associated with shorter survival), UCHL1 and TDP-43 (both increased in ALS patients). The involvement of microglia and astrocytes to ALS pathogenesis can be studied by measuring MCP-1 and GFAP respectively (4-6). Considering the mounting evidence implicating IFN-alpha signaling in the pathogenesis of ALS (7), we aim to comprehensively profile cytokines, neuroinflammatory markers, and neurodegeneration-related analytes in plasma and CSF from clinically characterized ALS patients and healthy controls. Biomarker investigation will be performed in a retrospective cohort of 31 ALS patients compared with 29 healthy subjects.

The samples to be analyzed in this study were obtained from a single visit and there is no planned longitudinal analysis component as part of this current study. Thus, this project is an initial exploratory biomarker study aimed to use established ALS fluid biomarkers as a benchmark to identify further potential hypothesis-driven candidate biomarkers within the IFN-alpha pathway. Promising candidate biomarkers will not be correlated against disease progression (since there are no follow-ups), but will be considered alongside the available clinical data and clinical outcome measures provided by the principal physician.

This study aims to support the initial validation of IFN-alpha pathway activation as a therapeutic target and explore its association with disease phenotype to provide insights into potential diagnostic and prognostic biomarkers for ALS, facilitating future therapeutic development.

4. OBJECTIVES AND ENDPOINTS

Objectives	Endpoints	Time point(s)
Primary Objectives To validate established ALS-related fluid biomarker levels within the sample cohort.	Primary Endpoint To evaluate levels of established fluid ALS biomarkers such as Nf-L, GFAP, and pTau (T181) in plasma and CSF of ALS patients vs. healthy controls.	Blood and CSF sampling at day 0
Secondary Objectives To identify hypothesis-driven novel fluid biomarkers in ALS related to the IFN-alpha pathway.	Secondary Endpoints To evaluate expression of candidate disease biomarkers in plasma in a cohort of ALS patients. To evaluate expression of candidate disease biomarkers in CSF in a cohort of ALS patients. To compare candidate disease biomarkers specificity and sensitivity with Nf-L, the benchmark biomarker for ALS	Blood and CSF sampling at day 0

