7. STUDY OBJECT

[figure not shown]
PROCEDURE	
Procedure(s)	Biomarker analysis Ulysses Neuroscience Ltd. will perform electrochemiluminescence sandwich ELISA using the Meso-Scale Discovery platform (MESO QuickPlex SQ 120 instrument and analyzed by Discovery Workbench 4.0 software). Samples will be analyzed in parallel using the NULISAseq™ proteomic platform (Alamar Biosciences) for confirmatory analysis of analyte expression using a secondary platform. Data will be analysed as ALS vs healthy control as raw values of each analyte in the samples (pg/mL) and graphed using GraphPad Prism v.9. Specific analytes to be measured include: a) U-Plex Immuno-Oncology Custom: IFN- α 2a, IFN- β , IL-12/IL-23p40, CXCL10/IP10, CCL2/MCP1. b) U-Plex Immuno-Oncology Custom: IFN- γ , IL-6, IL-8, IL-13, TNF- α , CCL5/RANTES. c) R-Plex Human TDP-43: TDP-43. d) S-Plex Neurology Panel 1: GFAP, Neurofilament L, Tau [Total]. e) S-Plex Human Tau: pTau T181 f) S-Plex Human Tau: pTau T217 g) S-Plex Human Tau: pTau T231 h) NULISAseq™ CNS Disease Panel 120 i) NULISAseq™ Inflammation Panel 250 AQ

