8. SAMPLE SIZE AND SUBJECT IDENTIFICATION

Sample Size

This proposed retrospective fluid biomarker study includes a sample size of 29 control and 31 ALS patient samples. Plasma and CSF samples were selected from healthy control individuals in order to ensure that two age-homogeneous groups were selected, based on the general age distribution of the ALS patient cohort (Healthy Control: 55 ± 12.47 years; ALS: 56.58 ± 13.46 years at time of sampling).

Sample sizes were selected based on our previous work and current scientific literature. In a prior study completed in collaboration with [name] group at SRH investigating Charcot-Marie-Tooth disease type 1A (CMT1A), we used a comparable number of control and patient samples (n=31 and 45, respectively) to analyse neurofilament light chain (Nf-L) levels in plasma. This study yielded a highly significant increase in Nf-L levels in CMT1A patient plasma compared to healthy controls ($p<0.0001$), demonstrating the suitability of this sample size for detecting biologically meaningful effects in peripheral nervous system degenerative disease.

[figure not shown]

Nf-L is increased in the plasma of CMT1A patients

- Plasma concentrations (pg/mL) of neurofilament light chain (Nf-L) in healthy control (n=31) and CMT1A patients (n=45) analysed by MSD electrochemiluminescence sandwich ELISA. Plasma Nf-L was significantly elevated in CMT1A patients compared to healthy controls ($p=0.0001$).

Given this experience, as well as data from published ALS biomarkers studies, we are confident our current sample size is appropriate for detecting group differences in established biomarkers such as Nf-L, GFAP, and pTau (T181) in ALS (8-11). Additionally, we are using data from published literature to inform expectations for other analytes included in the proposed analysis panel, such as inflammatory cytokines, markers of neurological disorder, and different phospho-tau species. However, we acknowledge that published data on many of these biomarkers in ALS are limited or inconsistent, underscoring the importance of investigating these analytes within this study.

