Furthermore, sample sizes were established based on Cohen's d power analysis performed based on published meta-analyses of case-control studies reporting effect sizes, or mean or standardised mean difference (SMD) for the benchmark ALS biomarker, Nf-L, in ALS CSF and plasma compared to healthy controls. SMD is statistically equivalent to Cohen's d, in meta-analyses: CSF Nf-L = SMD 1.46, Plasma Nf-L = 1.35 (12). With an effect size (Cohen's d) of 1.06 employed combined with an alpha level of 0.002 (considering all 18 biomarkers) and a minimum power cutoff of 80%, the minimum sample size required to reach statistical power was given to be 30. Considering this power analysis, and that dropout rate is not a factor of consideration for these samples because they have been already collected, and there is no risk of in blood collection, sample volume, or people withdrawing from the study, a sample size of 31 was selected.

	 
Power Analysis performed to inform sample size selection for this study.
 
This study is designed as an exploratory biomarker investigation. Its goals are two-fold: (1) to validate established ALS biomarkers using this cohort, and (2) to assess a broad panel of additional analytes that may be dysregulated in ALS, with a view toward identifying promising candidates for further investigation. We believe that this approach is scientifically justified for an initial exploratory study and aligns with standard practice in early-phase biomarker research. Future studies based on the findings of this work will incorporate expanded cohorts and statistical power analyses derived from this foundational dataset.

Subject Identification	Pseudonymised: participants are identified by a unique coded identification number. This code maintains confidentiality and links the participant to their data without revealing their identity.

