All statistical analyses will be performed using GraphPad Prism v.9. Each analyte will be analyzed on an individual analyte-by-analyte basis by unpaired two-tailed t-test, without multiple comparisons performed between analytes as is standard during early-phase exploratory biomarker research.

While several of the proposed biomarkers to be analyzed show strong correlation with age, selecting two age- and gender-homogenous populations for ALS and control samples will mitigate any non-pathological age-related deviations in specific biomarker levels.

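### A secondary endpoint compares candidates' sensitivity and specificity with Nf-L, but the only planned biomarker analysis, a t-test per analyte, estimates neither and makes no comparison with Nf-L

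*Combined protocol and SAP*

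**What the plan says.** Section 4 gives three secondary endpoints. Two concern candidate levels in plasma and in CSF. The third is "To compare candidate disease biomarkers specificity and sensitivity with Nf-L, the benchmark biomarker for ALS".

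Section 9 gives the analysis: "Each analyte will be analyzed on an individual analyte-by-analyte basis by unpaired two-tailed t-test, without multiple comparisons performed between analytes". It also says "All statistical analyses will be performed using GraphPad Prism v.9". Section 7 describes the same contrast, ALS against healthy control, on raw pg/mL values. The other tests reported in Section 9 (Welch, paired and unpaired t-tests, and an F test) all concern age at sampling.

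Section 3 calls the established markers a benchmark but names no method for using them as one. Section 8 sizes the study for a difference in means. No section available for review contains an ROC curve, an AUC, a cut-off rule, an estimate of sensitivity or specificity, or a comparison of a candidate with Nf-L in the same participants.

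**The concern.** A t-test compares two group means. It does not classify anyone, so it yields no sensitivity or specificity. Run on one analyte at a time, it also yields no contrast between a candidate and Nf-L. Its mean difference and confidence interval are in pg/mL, which cannot be compared across analytes. Even a standardised difference is not sensitivity or specificity.

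The risk is that p-values get used instead. If a candidate and Nf-L are both significant, a reader may take the candidate to be as good as the benchmark, although one may discriminate clearly less well. No decision rule rests on this endpoint. What is at stake is either an endpoint left unanswered, or one answered with a cut-off and method picked after the data are seen, with 18 analytes in two fluids to choose from.

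**Working it through.** **Inputs from the plan**
- Group sizes: 29 controls and 31 ALS patients (Section 8).
- Sample-size assumptions: d = 1.06, alpha 0.002, 80% power, minimum n of 30 (Section 8).
- Nf-L standardised mean differences: 1.35 in plasma, 1.46 in CSF (Section 8).
- Two-sided unpaired t-test (Section 9).

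**Assumptions made here:** normal markers with equal variances; correlation between the two AUC estimates of 0 to 0.5. The documents support neither, so the results are illustrative.

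**1. The plan's own figure.** A two-sided noncentral-t calculation with d = 1.06, alpha 0.002 and 80% power gives 30 per group (power 80.1%). The normal approximation gives 28. The stated 30 reproduces, and power at 29 and 31 is 80.0%. This figure concerns a mean difference only.

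**2. What significance implies for discrimination.** The smallest significant observed d is t(1−α/2, 58) × √(1/29 + 1/31), and √(1/29 + 1/31) = 0.2583. Then AUC = Φ(d/√2), and sensitivity at 90% specificity = Φ(d − 1.2816).

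| Case | d | AUC | Sensitivity at 90% specificity |
|---|---|---|---|
| Just significant at 0.05 | 2.002 × 0.2583 = 0.517 | 0.643 | 22% |
| Just significant at 0.002 | 3.237 × 0.2583 = 0.836 | 0.723 | 33% |
| Sample-size effect | 1.06 | 0.773 | 41% |
| Nf-L, plasma | 1.35 | 0.830 | 53% |
| Nf-L, CSF | 1.46 | 0.849 | 57% |

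**3. How often both would be significant.** At 0.002, power is 80% for d = 1.06, 97% for d = 1.35 and 99% for d = 1.46. At 0.05 it is 98% for d = 1.06 and above 99.9% for Nf-L. A weaker candidate and Nf-L would usually both be significant.

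**4. What a direct comparison would deliver.** Take a candidate with d = 1.06. Let SE₁ and SE₂ be the Hanley-McNeil standard errors of the two AUCs, and r the correlation between the AUC estimates. The SE of the difference is √(SE₁² + SE₂² − 2r·SE₁·SE₂). Power is for a two-sided 0.05 test.

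| Fluid | AUC difference | SE₁ (Nf-L), SE₂ (candidate) | r | 95% CI half-width | Power |
|---|---|---|---|---|---|
| Plasma | 0.830 − 0.773 = 0.057 | 0.053, 0.060 | 0 | 0.158 | 11% |
| Plasma | 0.057 | 0.053, 0.060 | 0.5 | 0.112 | 17% |
| CSF | 0.849 − 0.773 = 0.076 | 0.050, 0.060 | 0 | 0.154 | 16% |
| CSF | 0.076 | 0.050, 0.060 | 0.5 | 0.110 | 27% |

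A simulation of the DeLong test (8,000 runs, correlation between the markers themselves of 0 to 0.6) gave similar power: 10.5% to 17.0% in plasma and 17.1% to 28.2% in CSF.

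**5. Sensitivity at an estimated cut-off.** Suppose the cut-off for 90% specificity is taken from the 29 controls and an ordinary exact 95% interval is then put on sensitivity. In simulation (20,000 runs, d from 1.06 to 1.46) that interval covered the true sensitivity only about 75% to 82% of the time, depending on the quantile rule. With linear interpolation, the cut-off's true specificity had a central 95% range of about 74% to 96%. An interval that treats the cut-off as fixed is therefore too narrow.

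**The case against.** The strongest reply is that the study is exploratory, defers powered work to later cohorts, and could not separate a good candidate from Nf-L anyway. This is one of three secondary endpoints, and the t-test does serve the primary endpoint and the other two. That stands as a limit on severity. It excuses low power and, at most, the lack of multiplicity control. It does not excuse a listed endpoint without a method. Low power is a reason to report estimates with intervals and call them descriptive.

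The remark in Section 9 about comparisons between analytes may mean only that p-values will not be adjusted. On either reading, no comparison with Nf-L is specified.

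Two cautions on the figures stand. The 0.002 level belongs to the sample-size calculation; Section 9 does not state it as a test threshold. At 0.05 the argument is stronger, because weaker markers pass. And the AUC and sensitivity values depend on normality with equal variances, which may not hold for raw concentrations.

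Finally, the plan calls its controls healthy, but Section 5 requires only that they have no diagnosed neurodegenerative or neuromuscular disease (apart from age and the listed acute and organ-failure exclusions). Any caveat about specificity should refer to that definition.

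**Conclusion.** The concern holds. The stated method cannot answer the third secondary endpoint, and this conclusion needs no distributional assumption. Under the equal-variance normal model, a marker can be significant with an AUC of 0.64 (at 0.05) or 0.72 (at 0.002), against 0.83 to 0.85 for Nf-L, so t-test results cannot stand in for the comparison. The endpoint is exploratory and nothing is decided on it, so this should be corrected but does not undermine the primary objective. At this sample size, a proper comparison can only be descriptive.

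**What to change.** Add a short paragraph to Section 9, applied separately to plasma and CSF and labelled descriptive:

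- Report the ROC AUC with 95% CI for each candidate and for Nf-L.
- Report the paired AUC difference from Nf-L in the same participants with 95% CI, by DeLong or a paired bootstrap.
- If sensitivity is reported at a pre-set specificity or a data-derived cut-off, use a bootstrap that re-estimates the threshold in each resample. Correct a data-derived cut-off for optimism.
- Do not infer equivalence to Nf-L from a non-significant difference or from t-test p-values.
- State that specificity means against the controls defined in Section 5. There is no disease-control group, so the study cannot address the objection to Nf-L in Section 3, that its increase "represents a late pathogenic event also found in other neurological disorders besides ALS".

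The alternative is to reword the endpoint to what the t-tests can show, namely group differences in candidate levels.

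The first option costs some protocol wording, modest analysis time and possibly software beyond the one package named. It needs no further samples or participants. Its drawback is imprecision: 95% CI half-widths of about 0.11 to 0.16 on the AUC difference. Power to separate a d = 1.06 candidate from Nf-L is about 11% to 17% in plasma and 16% to 27% in CSF, as the assumed correlation between AUC estimates rises from 0 to 0.5.

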5. INCLUSION/EXCLUSION CRITERIA

a. Inclusion Criteria

Inclusion criteria for ALS patients:

- Age equal or over 18 years old
- ALS patients, diagnosed accordingly to the revised El Escorial Criteria

Disease duration <24 months from symptom onset.

Inclusion criteria for controls

- Age equal or over 18 years old
- Subjects without a diagnosis of neurodegenerative disease or neuromuscular disorder.

b. Exclusion Criteria

Exclusion criteria for ALS patients:

- FVC <60%;
- nutritional or respiratory failure; Significant hepatic or chronic renal failure or any intervening infective (**pneumonia, flu-like syndromes, urinary tract infections**) or metabolic (**acute renal failure, hyperosmolar hyperglycaemic state, severe hyponatremia**) conditions **present at the time of assessment that could potentially affect biomarker levels**.
- ALS patients exhibiting any of these conditions at the time of biofluid sampling as per the Case Report Form (CRF) will be excluded from sample selection.

Exclusion criteria for controls:

- Significant hepatic or chronic renal failure or any intervening infective (**pneumonia, flu-like syndromes, urinary tract infections**) or metabolic (**acute renal failure, hyperosmolar hyperglycaemic state, severe hyponatremia**) conditions **present at the time of assessment that could potentially affect biomarker levels**.
- Controls exhibiting any of these conditions at the time of biofluid sampling as per the Case Report Form (CRF) will be excluded from sample selection.

6. INFORMED CONSENT

Plasma and CSF were collected accordingly to clinical practice indication (GCP). ALS patients whose clinical data (demographic, epidemiological, family history of disease and neurological history of the patient) and biological samples (plasma and CSF for biomarker dosage) have already been collected, after informed consent (protocollo Banca Inspe), from the creation of the INSPE BANK and stored as per specific regulation will be included retrospectively.

This research is aimed at improving the health of people belonging to the same age group or who suffer from the same pathology or who are in the same conditions and the research program is subject to a motivated favourable opinion from the EC. The research does not involve significant risks to the dignity, rights, and fundamental freedoms of the interested party.

7. STUDY OBJECT

[figure not shown]
PROCEDURE	
Procedure(s)	Biomarker analysis Ulysses Neuroscience Ltd. will perform electrochemiluminescence sandwich ELISA using the Meso-Scale Discovery platform (MESO QuickPlex SQ 120 instrument and analyzed by Discovery Workbench 4.0 software). Samples will be analyzed in parallel using the NULISAseq™ proteomic platform (Alamar Biosciences) for confirmatory analysis of analyte expression using a secondary platform. Data will be analysed as ALS vs healthy control as raw values of each analyte in the samples (pg/mL) and graphed using GraphPad Prism v.9. Specific analytes to be measured include: a) U-Plex Immuno-Oncology Custom: IFN- α 2a, IFN- β , IL-12/IL-23p40, CXCL10/IP10, CCL2/MCP1. b) U-Plex Immuno-Oncology Custom: IFN- γ , IL-6, IL-8, IL-13, TNF- α , CCL5/RANTES. c) R-Plex Human TDP-43: TDP-43. d) S-Plex Neurology Panel 1: GFAP, Neurofilament L, Tau [Total]. e) S-Plex Human Tau: pTau T181 f) S-Plex Human Tau: pTau T217 g) S-Plex Human Tau: pTau T231 h) NULISAseq™ CNS Disease Panel 120 i) NULISAseq™ Inflammation Panel 250 AQ

8. SAMPLE SIZE AND SUBJECT IDENTIFICATION

Sample Size

This proposed retrospective fluid biomarker study includes a sample size of 29 control and 31 ALS patient samples. Plasma and CSF samples were selected from healthy control individuals in order to ensure that two age-homogeneous groups were selected, based on the general age distribution of the ALS patient cohort (Healthy Control: 55 ± 12.47 years; ALS: 56.58 ± 13.46 years at time of sampling).

Sample sizes were selected based on our previous work and current scientific literature. In a prior study completed in collaboration with [name] group at SRH investigating Charcot-Marie-Tooth disease type 1A (CMT1A), we used a comparable number of control and patient samples (n=31 and 45, respectively) to analyse neurofilament light chain (Nf-L) levels in plasma. This study yielded a highly significant increase in Nf-L levels in CMT1A patient plasma compared to healthy controls ($p<0.0001$), demonstrating the suitability of this sample size for detecting biologically meaningful effects in peripheral nervous system degenerative disease.

[figure not shown]

Nf-L is increased in the plasma of CMT1A patients

- Plasma concentrations (pg/mL) of neurofilament light chain (Nf-L) in healthy control (n=31) and CMT1A patients (n=45) analysed by MSD electrochemiluminescence sandwich ELISA. Plasma Nf-L was significantly elevated in CMT1A patients compared to healthy controls ($p=0.0001$).

Given this experience, as well as data from published ALS biomarkers studies, we are confident our current sample size is appropriate for detecting group differences in established biomarkers such as Nf-L, GFAP, and pTau (T181) in ALS (8-11). Additionally, we are using data from published literature to inform expectations for other analytes included in the proposed analysis panel, such as inflammatory cytokines, markers of neurological disorder, and different phospho-tau species. However, we acknowledge that published data on many of these biomarkers in ALS are limited or inconsistent, underscoring the importance of investigating these analytes within this study.

Furthermore, sample sizes were established based on Cohen's d power analysis performed based on published meta-analyses of case-control studies reporting effect sizes, or mean or standardised mean difference (SMD) for the benchmark ALS biomarker, Nf-L, in ALS CSF and plasma compared to healthy controls. SMD is statistically equivalent to Cohen's d, in meta-analyses: CSF Nf-L = SMD 1.46, Plasma Nf-L = 1.35 (12). With an effect size (Cohen's d) of 1.06 employed combined with an alpha level of 0.002 (considering all 18 biomarkers) and a minimum power cutoff of 80%, the minimum sample size required to reach statistical power was given to be 30. Considering this power analysis, and that dropout rate is not a factor of consideration for these samples because they have been already collected, and there is no risk of in blood collection, sample volume, or people withdrawing from the study, a sample size of 31 was selected.

	 
Power Analysis performed to inform sample size selection for this study.
 
This study is designed as an exploratory biomarker investigation. Its goals are two-fold: (1) to validate established ALS biomarkers using this cohort, and (2) to assess a broad panel of additional analytes that may be dysregulated in ALS, with a view toward identifying promising candidates for further investigation. We believe that this approach is scientifically justified for an initial exploratory study and aligns with standard practice in early-phase biomarker research. Future studies based on the findings of this work will incorporate expanded cohorts and statistical power analyses derived from this foundational dataset.

Subject Identification	Pseudonymised: participants are identified by a unique coded identification number. This code maintains confidentiality and links the participant to their data without revealing their identity.

